**Table ABEX.3. Estimated Precision Rates**

Sample Size	Estimated Proportion	Standard Error	Width of Proportion to 95% Confidence Limit	Width of Interval (2 sides)	95% Lower Confidence Limit	95% Upper Confidence Limit
250	11%	2.0%	3.9%	7.80%	7.1%	14.9%
250	30%	2.9%	5.7%	11.40%	24.3%	35.7%
200	11%	2.2%	4.3%	8.60%	6.7%	15.3%
200	30%	3.2%	6.4%	12.80%	23.6%	36.4%

### **5.3. End of Study Definition**

End of the study is the date of the last visit or last scheduled procedure shown in the Schedule of Activities (Section 2) for the last subject.

### **5.4. Scientific Rationale for Study Design**

The ELEMENT 5 study has proven the noninferiority of Basaglar administered QD to LANTUS administered QD, as measured by change in HbA1c level from baseline to 24 weeks, when used in combination with OAMs. Basaglar received marketing approval as a basal insulin for the treatment of type 1 diabetes and T2DM in India in 2017 in subjects above 2 years of age. Biosimilar guidelines (effective August 2016) recommend the safety of the biosimilar to be

evaluated in at least 300 subjects. There were 100 subjects from India in the ELEMENT 5 study. As a clause towards marketing approval, the DCGI recommended that Basaglar be studied in a minimum of 200 additional local subjects without specific guidance towards objective of the study from an efficacy or safety perspective.

Patients with T2DM who are unable to meet glycemic targets in spite of being on OAMs and/or GLP-1 RA and need to initiate basal insulin, are usually preferred for treatment with Basaglar. Hence, it was decided to conduct the study in these patients.

Thus we designed a multicenter, open-label, single-arm, Phase 4 study to assess the safety and efficacy of Basaglar in subjects with T2DM who are on  $\geq 2$  OAMs and/or GLP-1 RA and are insulin-naïve with inadequate glycemic control.

## 5.5. Justification for Dose

The American Diabetes Association (2018) recommends initiation of basal insulin at 10 units or 0.1 to 0.2 unit/kg/day depending on the degree of hyperglycemia. Subjects can self-titrate once or twice in a week by 2 to 4 units or 10% to 15% to reach the target FBG level of  $<100$  mg/dL (5.6 mmol/L). In case of hypoglycemia, the dose can be reduced by 4 units or 10% to 20%. The American Association of Clinical Endocrinologists consensus statement of 2018 recommends initiation of basal insulin based on HbA1c level of 8% (total daily insulin dose: 0.2 to 0.3 unit/kg). Thus, in this study the starting dose will be 10 units QD and the dose may be titrated every 2 to 3 days to reach the glycemic goal.

## 6. Study Population

Prospective approval of protocol deviations to recruitment and enrollment criteria, also known as protocol waivers or exemptions, are not permitted.

### 6.1. Inclusion Criteria

Subjects are eligible to be included in the study only if they meet all of the following criteria at screening:

- [1] have T2DM based on the disease diagnostic criteria from the World Health Organization (WHO) classification ([Appendix 6](#)) for at least 6 months before screening
- [2] men or non-pregnant women aged more than 18 years and less than 75 years at the time of screening
- [3] have been receiving GLP-1 RA or  $\geq 2$  OAMs at stable doses for 90 days prior to Visit 1
- [4] have an HbA1c level  $\geq 7.0\%$  and  $< 11.0\%$
- [5] have never been treated with insulins except for short term treatment of acute conditions up to a maximum of 14 days
- [6] are able and willing to provide signed informed consent to participate in this study in accordance with local regulations

### 6.2. Exclusion Criteria

Subjects will be excluded from study enrollment if they meet any of the following criteria at screening:

- [7] have any form of diabetes other than T2DM
- [8] have hypersensitivity to the active substance of Basaglar or to any of the excipients
- [9] have any clinically significant disorder, other than T2DM, that in the investigator's opinion, would preclude participation in the trial
- [10] are receiving systemic glucocorticosteroids therapy or have excessive insulin resistance (total insulin dose  $> 2$  U/kg)
- [11] have a history or diagnosis of human immunodeficiency virus infection, hepatitis B and C
- [12] have comorbidities of unstable angina, cardiac failure (Stage III or IV as per New York Heart Association guidelines) or renal failure (estimated glomerular filtration rate  $< 30$  mL/min/m^2)
- [13] are pregnant or intend to become pregnant during the course of the study; or are sexually active women of child-bearing potential not actively practicing birth control by a medically acceptable method as determined by the investigator
- [14] is a woman who is breastfeeding
- [15] are investigator site personnel directly affiliated with this study and/or their immediate families. Immediate family is defined as spouse, parent, child, or sibling, whether biological or legally adopted
- [16] are Lilly employees or are employees of third party organizations involved in the study who require exclusion of their employees

- [17]have participated within the last 30 days in a clinical trial involving an investigational product other than the Basaglar. If the previous investigational product has a long half-life, 3 months or 5 half-lives (whichever is longer) should have passed
- [18]have previously completed or withdrawn from this study or any other study investigating Basaglar. This exclusion criterion does not apply to subjects who are rescreened prior to baseline visit
- [19]are currently enrolled in any other clinical study involving an investigational product or any other type of medical research judged not to be scientifically or medically compatible with this study
- [20]are unwilling or unable to comply with the use of a glucometer

### **6.2.1. *Rationale for Exclusion of Certain Study Candidates***

Exclusion criteria [7], [8], [10], and [12] exclude medications or conditions that may cause HbA1c lowering not attributable to the regimens being studied or which could lead to misinterpretation of the results.

Exclusion criterion [9] permits investigators to exclude subjects who meet all other inclusion and exclusion criteria but may not be appropriate for this study.

Exclusion criterion [11] may prevent subjects from completing the protocol, may influence the effect or safety of study regimens.

Exclusion criteria [13] and [14] ensure the safety of unborn and newborn children.

Exclusion criteria [15] and [16] reduce potential bias due to conflict of interest.

Exclusion criteria [17], [18], [19], and [20] prevents a situation in which potential positive or negative outcomes may not be clearly attributable to the regimens in the study.

### **6.3. *Lifestyle Restrictions***

Patients will be suggested to continue their usual exercise habits and generally follow a healthy meal plan throughout the course of the study.

### **6.4. *Screen Failures***

Individuals who do not meet the criteria for participation in this study (screen failure) at the initial visit may be later rescreened only once. The interval between screening and rescreening should be at least 4 weeks. A new informed consent form (ICF) must be signed at the time of rescreening and the study participant will be assigned a new identification number. A single repeat testing of suspected erroneous/spurious central laboratory results is allowed without rescreening the study participant. These will be done in consultation with the Lilly clinical research physician (CRP).

## 7. Treatments

### 7.1. Treatments Administered

Subjects will receive Basaglar QD at bedtime. The starting dose will be 10 units. Subjects can self-titrate as outlined in [Table ABEX.4](#) once or twice weekly until FBG is lowered to <100 mg/dL (5.6 mmol/L). In case of hypoglycemia, the dose can be reduced by 4 units. Subjects will continue their pre-study anti-diabetic medications at the prescribed dosage throughout the study except for risks described in Section [7.7](#). It is recommended that doses of anti-diabetic medications being taken by the subjects is stable for 90 days prior to enrolling them in this study. However, the investigator can recommend that these doses be optimized to maximum tolerated dose during 2 weeks of the screening period. If the target FBG levels are not achieved at Visit 2, the subjects are included in the study and Basaglar is initiated.

**Table ABEX.4. Recommendations for Dose Titrations**

Fasting Blood Glucose (mg/dL)	Fasting Blood Glucose (mmol/L)	Dose Adjustments (Units)
<80	<4.4	-2
80-100	4.4-5.6	0
101-130	5.6-7.2	+2
131-160	7.3-8.9	+4
161-190	8.9-10.6	+6
>190	>10.6	+8

The investigator or his or her designee is responsible for

- explaining the correct use of the investigational agent to the subject
- verifying that instructions are followed properly
- maintaining accurate records of investigational product dispensing and collection, and
- returning all unused medication to Lilly or its designee at the end of the study, unless the sponsor and sites have agreed all unused medication is to be destroyed by the site, as allowed by local law.

#### 7.1.1. Packaging and Labelling

Clinical study materials will be labeled according to the country's regulatory requirements.

### **7.1.2. Medical Devices**

Glucometers, test strips, and lancets will be provided to patients. Patients will be trained to use glucometers to self-monitor the blood glucose levels as specified in the Schedule of Activities (Section 2).

## **7.2. Method of Treatment Assignment**

Patients who meet all criteria for enrollment will be assigned to Basaglar treatment.

### **7.2.1. Selection and Timing of Doses**

Subjects will self-administer the insulin every day at bedtime after dinner. Patients will record the actual time and dose of all administrations of Basaglar in the subject diary. Later, these data will be recorded in the subjects' electronic case report form (eCRF).

## **7.3. Blinding**

This is an open-label study. The investigational product will be procured from commercially available Basaglar in India. The investigational product will be adequately labeled to indicate that it is only for use in the clinical study and is not for sale.

## **7.4. Dosage Modification**

The doses may be titrated by 2 to 4 units once or twice in a week until FBG levels are lowered to <100 mg/dL (5.6 mmol/L) as tabulated in [Table ABEX.4](#).

Investigators will be trained to assess when they need to intervene the treatment regimen of subjects who do not reach glycemic targets. If any of the FBG values for 2 consecutive weeks exceed the limits outlined below with no other possible cause of hyperglycemia, rescue medication (more OAMs or GLP-1 RA or bolus insulin; switching to a different basal insulin is not permitted as decided by the investigator) will be prescribed in addition to the ongoing treatment.

- FBG >270 mg/dL (>15.0 mmol/L) from baseline to Week 6 (4 values/week)
- FBG >240 mg/dL (>13.3 mmol/L) from Week 6 to Week 12 (4 values/week)
- FBG >200 mg/dL (>11.1 mmol/L) from Week 12 to end of trial (4 values/week)
- HbA1c  $\geq 8.5\%$  ( $\geq 69.4$  mmol/mol) by and after Week 24

The dose and name of rescue medication must be properly documented in the eCRF. Subjects who had to use rescue medication during the study period will be excluded from the per protocol set (PPS) population.

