## 5. Study Design

### 5.1. Overall Design

Study I4L-IN-ABEX (ABEX) is a multicenter, open-label, single-arm, Phase 4 study to assess the safety of Basaglar in subjects with T2DM in India.

The study design includes the following periods:

[figure not shown]
- Screening (Week -2 to Week 0)
- Treatment
  - Titration period (Week 0 to Week 12)
  - Maintenance period (Week 12 to 24)
- Safety Follow-up (Week 28)

Week 0 to Week 12 will be the titration phase followed by the maintenance phase till Week 24. Approximately 295 subjects will be screened as per the inclusion and exclusion criteria mentioned in Sections [6.1](#) and [6.2](#), respectively, so that 250 subjects can be enrolled in the study, with a target to have a minimum of 200 subjects completing the present study. Subjects will be screened at Visit 1 and eligible subjects will be administered with Basaglar once daily (QD) from Visit 2 for a period of 24 weeks.

The starting dose will be 10 units QD. All subjects will be trained at Screening (Visit 1) on insulin injection administration technique, use of glucometer, and 7-point SMBG measurement. These trainings will be reinforced at every face-to-face visit of the treatment period. Subjects will self-administer Basaglar at bedtime. The doses may be titrated by 2-4 units once or twice in a week until FBG levels are lowered to <100 mg/dL (5.6 mmol/L).

Study governance considerations are described in detail in [Appendix 3](#).

Figure [ABEX.1](#) illustrates the study design.

\*Telephone visit

Abbreviations: GLP-1 RA = glucagon-like peptide-1 receptor agonist; OAM = oral antihyperglycemic medications; QD = once daily.

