#### Treatment period (Week 0 to Week 24)

Study participants found eligible during the screening period will begin their treatment at Visit 2. All measures to be performed at Visit 2 will be done prior to administration of Basaglar. All necessary trainings will be imparted at Visits 1 and 2 and will be reinforced at subsequent visits as outlined in Section 2.

Subjects will be instructed to carry the glucometers to the sites at Visits 2, 3, 4, 5, and 8. Subjects will be instructed to measure and record the FBG levels daily before the morning meal till Week 12. Also, subjects will be instructed to measure and record the blood glucose levels if they have symptoms of hypoglycemia at any time of the day or night. Subjects will be instructed to perform 7-point self-monitored blood glucose (SMBG) level monitoring (glucose measurements before breakfast, lunch, and dinner; 2 hours after breakfast, lunch, and dinner; and at 3 am [ $\pm$  1 hour]) 2 to 3 days in the week prior to Visits 2, 3, 4, 5, and 8 and record the values in the subject diary (Section 2).

Subjects will self-administer Basaglar QD at bedtime. They will self-titrate once or twice in a week until FBG levels are lowered to  $<100$  mg/dL (5.6 mmol/L).

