4.1 Design overview

This is a multicenter, open-label, single-arm, phase 4 study to assess the safety of Basaglar in insulin-naïve subjects with T2DM in India. The study period consists of a screening period (Week -2 to Week 0), a treatment period (Week 0 to Week 24), and a safety follow-up visit at Week 28.

Treatment period contains Week 0 to Week 12 will be the titration phase followed by the maintenance phase till Week 24. Approximately 295 subjects will be screened as per the inclusion and exclusion criteria mentioned in Sections 6.1,(in protocol) and 6.2,(in protocol) respectively, so that 250 subjects can be enrolled in the study, with a target to have a minimum of 200 subjects completing the present study. Subjects will be screened at Visit 1 and eligible subjects will be administered with Basaglar once daily (QD) from Visit 2 for a period of 24 weeks. In this study, we would seek to understand the safety of this drug in the local Indian population in accordance with the biosimilar guidelines of India. Subjects will self-administer Basaglar once daily at bedtime (starting dose will be 10 units). Subjects can self-titrate (as per outlined in table 4.1) 2-4 units once or twice in weekly until FBG levels are lowered to <100 mg/dL (5.6 mmol/L). In case of hypoglycemia, the dose can be reduced by 4 units. Subjects will continue their pre-study anti-diabetic concomitant medications.

This is a single-arm study and enrolled subjects will be treated with Basaglar using a self-titration scheme as outlined in below table 4.1.

| Fasting Blood Glucose (mg/dL) | Fasting Blood Glucose (mmol/L) | Dose Adjustments (Units) |
|-------------------------------|-----------------------------------|--------------------------|
| <80 | <4.4 | -2 |
| 80-100 | 4.4-5.6 | 0 |
| 101-130 | 5.6-7.2 | +2 |
| 131-160 | 7.3-8.9 | +4 |
| 161-190 | 8.9-10.6 | +6 |
| >190 | >10.6 | +8 |

Table 4.1

No randomization will be performed as this is a single-arm study. The sample size was calculated assuming a 15% screen failure rate, with a target to have a minimum of 200

subjects completing the study. No interim analyses and/or sample size re-estimation are planned to be performed.

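### The insulin self-titration instructions contradict each other on step size above 160 mg/dL and on frequency, in a trial whose primary endpoint is hypoglycaemia

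*Protocol*

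**What the plan says.** **Step size.** Protocol 5.1 states: "The doses may be titrated by 2-4 units once or twice in a week until FBG levels are lowered to" a target of below 100 mg/dL. Protocol 7.4 opens in the same way, "The doses may be titrated by 2 to 4 units once or twice in a week", and then refers the reader to the table headed "Table ABEX.4. Recommendations for Dose Titrations". That table gives 0 at FBG 80-100 mg/dL, +2 at 101-130, +4 at 131-160, +6 at 161-190 and +8 above 190. The Synopsis prints the same scheme. SAP 4.1 combines the two in one sentence: it cites its own Table 4.1, which has identical rows, and adds "2-4 units once or twice in weekly until FBG levels are lowered to" the same target.

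**Frequency.** Protocol 5.1, 7.1 and 7.4 and SAP 4.1 say once or twice a week. So does the treatment-period text in Protocol 5.1.1: "They will self-titrate once or twice in a week until FBG levels are lowered to" target. Protocol 5.5, in a sentence that is expressly about this study, says "the dose may be titrated every 2 to 3 days to reach the glycemic goal".

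**Reduction.** The table's only decrease is 2 units, for any FBG below 80 mg/dL. Protocol 7.1 adds "In case of hypoglycemia, the dose can be reduced by 4 units", and SAP 4.1 repeats this.

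**Context.** Subjects titrate themselves. At visits, site staff review dose and FBG and may recommend a change (Schedule of Activities). The primary endpoint is the incidence of hypoglycaemic events, and basal insulin dose is a secondary endpoint (Protocol 4). Protocol 7.6 lists the titration algorithm among the things by which compliance is assessed. It also treats as withdrawn a subject whom the investigator judges to have intentionally or repeatedly taken more insulin than prescribed.

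**The concern.** Section 7.4 cannot be followed as written when FBG exceeds 160 mg/dL. It sets a step of 2 to 4 units and, in the same sentence, sends the reader to a table whose entry at that glucose level is 6 or 8. A subject or site that follows the sentence and one that follows the table will raise the dose at different speeds. The frequency in 5.5 adds a second, separate disagreement.

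Two things are at stake. First, insulin exposure is itself a secondary endpoint and is the treatment whose hypoglycaemia risk the trial exists to describe. If exposure depends on which section is used, the reported incidence does not belong to one defined regimen, and there is no control arm titrated under the same instructions to compare with. Secondly, above 160 mg/dL the same behaviour can be correct under the table and above the prescribed step under the text. That leaves the titration-algorithm item and the excess-dose clause in 7.6 ambiguous.

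**Working it through.** The plan gives no figure for weekly dose change, so there is none to reproduce. The inputs are its own titration rules.

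**Inputs**
- Starting dose: 10 units once daily (Protocol 7.1, "The starting dose will be 10 units").
- Step under the text: 2 to 4 units (Protocol 5.1, 7.4; SAP 4.1).
- Step under the table: +2, +4, +6 or +8 by FBG band (Table ABEX.4; SAP Table 4.1).
- Frequency: 1 or 2 a week (Protocol 5.1, 5.1.1, 7.1, 7.4; SAP 4.1), or one change every 2 to 3 days (Protocol 5.5).

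**1. Step size at a common pace.** Weekly change = units per step × steps per week. At two steps a week:

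| FBG (mg/dL) | Text, at most | Table |
|---|---|---|
| 101-130 | 2 × 4 = 8 U/week | 2 × 2 = 4 U/week |
| 131-160 | 2 × 4 = 8 U/week | 2 × 4 = 8 U/week |
| 161-190 | 2 × 4 = 8 U/week | 2 × 6 = 12 U/week |
| above 190 | 2 × 4 = 8 U/week | 2 × 8 = 16 U/week |

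In the first two bands the table's step lies within the 2-4 unit range, so text and table agree. The conflict begins above 160 mg/dL. Above 190 the table's weekly increase is 16/8 = 2 times the text's ceiling.

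**2. Illustration.** Assume that FBG stays above 190 mg/dL for two weeks, with two steps a week:
- Text maximum: 10 + 2 × 8 = 26 U.
- Table: 10 + 2 × 16 = 42 U.

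**3. Frequency.** Every 3 days is 7/3 = 2.3 steps a week; every 2 days is 7/2 = 3.5. The range 2.3-3.5 does not overlap with 1-2.

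**4. Reduction.** The two rules have different triggers: FBG below 80 mg/dL for the table, hypoglycaemia for the sentence in 7.1. They meet at one place. Under Protocol 9.1.1 a fasting value of 54 mg/dL or less is a hypoglycaemic event, and it also lies in the table's lowest row. There the documents give both 2 and 4 units and do not say which takes precedence.

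**5. Compliance.** SAP 13.1 derives compliance status from the missed-dose questions alone, and the numeric criteria in Protocol 7.6 are also missed days. Neither depends on the titration rule. Only the titration-algorithm item and the investigator-judged excess-dose clause do.

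**The case against.** The strongest reply is that the table is evidently the operating schedule. The Synopsis and 7.1 present it without a 2-4 unit range, 7.4 and SAP 4.1 both refer to it, and the text only says that doses may be titrated. Section 5.5 is a dose-justification section and the only one with a different frequency. Subjects receive self-titration training that is repeated at every treatment visit, and investigators receive start-up training, so practice may be more uniform than the text. The training materials are not among the documents, so divergence between subjects or sites is possible but not shown.

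Much of this is fair, but it does not remove the conflict. Three sections state 2-4 units, two of them while citing a table that exceeds it, and no section says that the table prevails. Section 5.5 cannot be set aside as guideline background, because its sentence states what will be done in this study. Nor is the disputed range remote: every FBG threshold for rescue medication in 7.4 (above 270, 240 and 200 mg/dL) lies in the table's +8 row.

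The reply is right about the reduction rules. A reader might infer that 2 units and 4 units flatly contradict each other. The 4-unit sentence is permissive and has its own trigger, and 7.8.3 leaves reduction after severe events to the algorithm or the investigator. Only the precedence at fasting values of 54 mg/dL or below is missing.

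It is also right that some spread is intended. The text alone allows from 1 × 2 = 2 to 2 × 4 = 8 U/week.

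**Conclusion.** The step-size and frequency instructions are inconsistent in the current protocol, and the step-size conflict recurs in the SAP. The step-size conflict is confined to FBG above 160 mg/dL. At two steps a week it amounts to at most 8 versus 12 U/week at 161-190 and at most 8 versus 16 U/week above 190. The 26 U versus 42 U comparison rests on FBG staying above 190 for two weeks; the documents give no FBG distribution to show how often that would happen. The unstated precedence between the reduction rules is minor.

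Three stronger readings are not supported:
- **An increase of 28 U/week.** A reader might multiply the table's +8 by 3.5 steps a week. No section joins these rules: 5.5 does not cite the table, and 7.1 and 7.4, which do, say once or twice weekly.
- **A known shift in the primary incidence.** The documents contain no relation between titration speed and hypoglycaemia, so neither the size nor the existence of a shift can be calculated. The precision figures in Table ABEX.3 are unaffected.
- **Compliance that cannot be assessed at all.** The missed-dose criteria stand. The ambiguity is limited to the algorithm item and the excess-dose clause, above 160 mg/dL.

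What remains still needs correction before use: instructions for self-administered insulin that cannot all be followed, in a trial that measures hypoglycaemia and insulin dose.

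**What to change.** The sponsor's clinical team must reconcile step size, frequency and the precedence of the reduction rules across the Synopsis, Protocol 5.1, 5.1.1, 5.5, 7.1, 7.4 and Table ABEX.4, and SAP 4.1 with its Table 4.1, so that one rule appears everywhere. The reconciled rule should then go to sites and into the patient training, and the algorithm item and excess-dose clause in 7.6 should be read against it. Which rule is right is a clinical decision, and none is proposed here.

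The cost is protocol and SAP wording and a clarification letter to sites. The sample size and the planned analyses do not change.
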